9 PHARMACOKINETICS AND PHARMACODYNAMICS

9.1 Pharmacokinetics

Pharmacokinetic data are only collected pre-dose on Days 1, 2 and 6 in Group A. Concentration data will be listed and summarized.

9.2 Pharmacodynamics

Plasma and serum samples were collected for summary and exploratory analysis as appropriate (e.g. compare change from baseline between the two treatment arms). Listings, summaries graphs and figures for raw values and change from baseline (if appropriate) over time will be generated. Associations with response may be explored.

10 SAFETY ANALYSES

All safety summaries and listings will be presented by treatment group and overall based on the SS as defined in in Section 3.5 unless otherwise stated.

10.1 Extent of exposure

Details of study treatment administration will be listed, including administration of the concomitant antibiotics, by treatment arm and participant, ordered by date of administration within participant. This listing will include all medications that are considered as SOC for Arm B. The actual endpoints to be listed will be defined in the TFL shells, but at a minimum should contain date and time of each dose of Zilucoplan® and concomitant antibiotics for participants on Arm A, and for each of the SOC medications and concomitant antibiotics for participants on Arm B.

Frequency counts and percentages for the number of doses of study treatment received and summary statistics for the duration of exposure to study treatment will be presented overall and broken down by age (<75yr, >=75yrs) and sex. Duration of exposure will be calculated as follows:

$$\textit{Duration of Exposure} = (\textit{Date of Last Dose} - \textit{Date of First Dose})$$

Antibiotics after discharge for the Zilucoplan® arm were not collected by day (due to be taken for 14 days after discharge) in the CRF. Hence for Day 28-31 just the information of ‘were antibiotics’ taken (Y/N) will be listed, but the detail of compliance in this period will not be able to be captured.

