8.1.5. Duration of treatment

14 days, or until hospital discharge, whichever comes first

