3.2 General study level definitions

3.2.1 Analysis time points

3.2.1.1 Relative day

The relative day of an event or assessment will be derived using the date/time of first dose of study treatment as reference. This is the date/time of first dose of Zilucoplan® for participants randomised to Arm A and first dose of IV antibiotic for participants randomised to Arm B.

For the purposes of reporting, there is no relative Day 0. Note that the protocol refers to 'Screening (D0 or D1)'. This is to indicate that it is expected that screening will only take 24 hours and ends at first dose on D1. However, for some participants this is two days (D0 and D1) and for others it is only 1 day (D1) Hence the SAP/TFLs will state 'Day -1' if the day before dosing and 'Day 1' if the day of dosing to ensure differentiation of the days.

Relative days for an event or assessment occurring before the date/time of first dose are calculated as follows and preceded by '-':

$$\text{Relative Day} = \text{Event/Assessment Date/Time} - \text{Date/Time of First Dose}$$

If Time has not been collected for the event/assessment, checks must be made to ensure that any Event/Assessment made on the same day, but PRIOR to first dose, is indicated as this will form part of the calculation to identify baseline values.

The relative day for an event or assessment occurring on or after the first dose to the date of the last dose of study treatment will be calculated as follows:

$$\text{Relative Day} = (\text{Event/Assessment Date} - \text{Date of First Dose}) + 1$$

For events or assessments occurring after the date of the last dose, relative day will be prefixed with ‘+’ in the data listings and will be calculated as follows:

$$\text{Relative Day} = \text{Event/Assessment Date} - \text{Date of Last Dose}$$

Relative day will not be calculated in cases where dates are partial and should be presented as “--” in the relevant data listing.

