3.5.3 Safety Set

The Safety Set (SS) will consist of all participants who have received at least 1 dose of Zilucoplan® on Arm A and all participants who have had at least one dose of IV prophylactic antibiotic on Arm B.

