The number and percentage of participants who discontinued due to AEs will be summarized separately for all participants, based on the FAS. This will be used for European Union Drug Regulating Authorities Clinical Trials (EudraCT) reporting.

In addition, the following listings will be presented:

- Study participant disposition (ES)
- Study discontinuation (ES)
- Analysis sets (ES)

The listing of study participant disposition will be presented by treatment group and by site, and will include the date of informed consent, date and time of first and last dose of study treatment, number of days on treatment, date of decision to terminate study treatment early and primary reason, date of D28 visit, date of the follow-up visit (if completed).

The number of days on study treatment will be calculated as follows:

$$\begin{aligned} & \textit{Number of Days on Study Treatment} \\ & = (\textit{Date of Last Dose Received} - \textit{Date of First Dose Received}) + 1 \end{aligned}$$

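### SAP 10.1 calculates duration of exposure one day short of the SAP's own inclusive day count, so a full 14-day Zilucoplan course is summarised as 13 days and a single dose as 0 (minor)

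*SAP*

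**What the plan says.** SAP 10.1 (Extent of exposure) states "Duration of exposure will be calculated as follows" and then gives the date of last dose minus the date of first dose, with no further term. On its use, the section says that "summary statistics for the duration of exposure to study treatment will be presented overall and broken down by age (<75yr, >=75yrs) and sex". The same sentence also calls for frequency counts and percentages of the number of doses received.

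SAP 5.1 (Participant disposition) states "The number of days on study treatment will be calculated as follows" and gives the date of last dose received minus the date of first dose received, plus 1. The result goes into the disposition listing, next to the first and last dose dates.

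SAP 3.2.1.1 (Relative day) numbers assessments from the first to the last dose as assessment date minus first dose date, plus 1. It states that reporting has no Day 0.

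Protocol 8.1.5 gives the treatment duration as "14 days, or until hospital discharge, whichever comes first". The protocol summary specifies once-daily dosing, and SAP 3.2.1.2 sets the planned active treatment from D1 up to D14. The Safety Set in SAP 3.5.3 covers, in Arm A, all "participants who have received at least 1 dose of Zilucoplan", so a participant with one dose is included.

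**The concern.** Two sections of one SAP measure time on treatment from the same two dates and give different answers. The 5.1 rule counts both the first and the last dosing day, which suits a once-daily drug whose first dose falls on Day 1. The 10.1 rule leaves one of those days out. Nothing in 10.1 calls the quantity an elapsed interval or explains the difference, and SAP 3.8, which lists departures from the protocol analyses, does not mention it.

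What is at stake is consistency within the report. For a participant who completes the course without a missed dose, 10.1 would put 14 doses beside 13 days, while the 5.1 listing would show 14 days. For a participant with one dose, it would put 1 dose beside 0 days. Treatment stops at discharge, so short courses are expected, and the relative error is largest there.

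**Working it through.** **Inputs**
- First dose on D1, once daily: protocol summary; SAP 3.2.1.1.
- Full course from D1 up to D14, called 14 days: SAP 3.2.1.2; protocol 8.1.5.
- At least one dose for the Safety Set: SAP 3.5.3.

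**Formulas**, with L the day of the last dose and F the day of the first:
- SAP 10.1: L − F
- SAP 5.1: (L − F) + 1
- SAP 3.2.1.1, relative day of the last dose: (L − F) + 1

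**Step 1. Reproduce the planned 14 days.** With F = 1 and L = 14:
- SAP 5.1 gives (14 − 1) + 1 = 14, which agrees with the plan.
- SAP 3.2.1.1 gives Day 14, which also agrees.
- SAP 10.1 gives 14 − 1 = 13, which does not.

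**Step 2. Other course lengths.** The relative shortfall is 1 divided by the inclusive count.

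| Course | SAP 10.1 | SAP 5.1 | Shortfall |
|---|---|---|---|
| D1 to D14 | 13 | 14 | 1/14 = 7.1% |
| D1 to D6 | 5 | 6 | 1/6 = 16.7% |
| Two doses, D1 and D2 | 1 | 2 | 1/2 = 50% |
| One dose | 0 | 1 | 1/1 = 100% |

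**Step 3. Effect on the summaries.** Every value falls by exactly 1. The mean, median, minimum and maximum therefore each fall by 1 day, overall and in each age and sex group, and the SD does not change. With mean inclusive durations mA and mB, the between-arm difference under 10.1 is (mA − 1) − (mB − 1) = mA − mB, so it is unchanged.

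**Step 4. Arm B.** SAP 3.2.1.1 fixes the first dose in this arm as the first IV antibiotic dose. The last dose is less clear: SAP 3.2.1.2 runs planned treatment in both arms up to D14, and SAP 5.1 describes up to 14 days of standard of care with one week of antibiotic. If the last dose is the last of the antibiotic week (L = 7), 10.1 gives 6 where 5.1 gives 7, a shortfall of 1/7 = 14.3%. If it is D14, the figures are 13 and 14, as in Arm A.

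**The case against.** The strongest case against the point concerns its consequence. SAP 10.1 tabulates dose counts next to the duration and lists the date and time of each Zilucoplan dose, and SAP 5.1 lists the inclusive day count. Nothing downstream uses the 10.1 figure. SAP 10.2 counts treatment-emergent events from first dose to the D28 visit and reports participants, percentages and event counts, with no exposure-adjusted rates. SAP 7 checks compliance from pharmacy and dispensing records. No efficacy model includes duration of exposure. All of this stands, and it is why the point is minor.

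The intent can also be questioned. The 10.1 formula has brackets with nothing after them, while the bracketed formulas in 5.1 and 3.2.1.1 are followed by the added 1. That fits a dropped term, either a typing slip or a loss in the PDF text, and the text alone cannot settle which. Alternatively, Table 8.1 in SAP 8.2 defines duration of hospital stay as a plain date difference, so the word duration could mean an elapsed interval. But 10.1 does not say so, and an elapsed interval would still give zero exposure to someone who was dosed. Either way the formula as printed conflicts with 5.1 and needs attention.

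A reader might infer three stronger things that the documents do not support:
- **That the report would lead people to think nobody completed the course.** The dose counts and the 5.1 listing would show otherwise.
- **That the missing day matters for the safety of the highest dose per kilogram**, since protocol 8.1.3 cites 7 days of human experience at 0.6 mg/kg. The exposure summary is split by age and sex, not by weight, and both 13 and 14 exceed 7.
- **That the full Arm B week is certainly reported as 6 days.** This needs the last antibiotic dose to be that arm's last dose, which the SAP does not settle.

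**Conclusion.** The inconsistency is real and follows directly from the formulas as printed. SAP 10.1 understates time on treatment by exactly one day for every participant, relative to SAP 5.1 and 3.2.1.1. In Arm A a full D1 to D14 course becomes 13 days (7.1% short) and a single dose becomes 0.

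The effect stays within a descriptive safety summary, where it disagrees visibly with the dose counts and the disposition listing. It alters no between-arm difference in mean duration, no adverse event rate and no efficacy result. Severity is minor.

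The conclusion assumes that the formula reads in the signed SAP as it does in the text and that 10.1 is meant to count days of treatment. The comparison with dose counts also assumes that no dose is missed between the first and the last.

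**What to change.** In SAP 10.1, define duration of exposure as (date of last dose − date of first dose) + 1, matching 5.1, and use it for the overall, age and sex summaries. If an elapsed interval was really intended, 10.1 should label it as one and explain why it differs from 5.1, but the inclusive count is the simpler choice.

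Adding 1 does not settle what ends exposure in Arm B. A short statement of which dose counts as that arm's last would make its figures interpretable.

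The cost is one term in one formula and, if wanted, one sentence on Arm B. It needs no new data and affects no other analysis.

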10.2 Adverse events

An AE is any untoward medical occurrence in a participant or clinical investigation participant administered a pharmaceutical product that does not necessarily have a causal relationship with this treatment. An AE can therefore be any unfavorable and unintended sign (including an abnormal laboratory finding), symptom, or disease temporally associated with the use of a medicinal (investigational) product, whether or not related to the medicinal (investigational) product.

AEs are further characterised as pre-treatment or treatment emergent.

A pre-treatment AE are events whose onset date and time is prior to the first administration of study drug (Zilucoplan® for Arm A and IV antibiotic for Arm B).

A TEAE is defined as any AE with a start date/time on or after the first dose of study treatment up until the D28 visit. Any AE with an onset date later than the D28 visit for a participant will not be considered as treatment-emergent and therefore will not be included in the tabulations of TEAEs. Where dates are missing or partially missing, AEs will be assumed to be treatment-emergent, unless there is clear evidence to suggest that the AE started prior to the first dose of study treatment. Missing or partially missing dates for AEs will be handled as described in [Section 4.2.3](#). All AEs for a participant will be recorded in the eCRF from the time of informed consent until completion or early study discontinuation.

For each AE the following information should be provided in the eCRF: AE term (verbatim), date and time of onset, whether or not the AE was classified as an SAE, relationship to study treatment, severity, action taken with study treatment, other action taken, outcome, date and time of outcome and whether the AE led to study treatment discontinuation or to study discontinuation.

COVID-19 infection is a very recent syndrome, on which few data are available. Therefore, normal symptoms and natural disease course symptoms that will not be reported as adverse events are dyspnea, coughing, malaise, fever, drop in oxygen saturation, progression to respiratory failure, progression to ARDS, drop in blood pressure. However, progression to multi-organ failure may have other etiologies and will be reported as an SAE.

The number and percentage of participants who experience TEAEs will be summarized by MedDRA preferred term (PT) and treatment.

Summaries of TEAEs may include the following:

- Incidence of overall TEAEs (overview including number and percentage of participants with any TEAEs, serious TEAEs, discontinuations due to TEAEs, drug-related TEAEs, severe TEAEs and TEAEs leading to death; event counts will also be included)
- Incidence of TEAEs
- Incidence of TEAEs by maximum intensity
- Incidence of TEAEs by maximum CTCAE grade
- Incidence of TEAEs by maximal relationship
- Incidence of non-serious TEAEs above reporting threshold of 5% of study participants

Summary tables will contain counts of study participant, percentages of study participants in parentheses and the number of events where applicable. A participant who has multiple events in the same SOC and PT during a given treatment will be counted only once in the participant counts for that treatment, but all events will be included.

In summaries including relationship, the following relationships will be summarized: Any, 'Not related', 'Related'. eCRF entries of 'Not applicable' and 'Unlikely' will be classified as 'Not

Related'. eCRF entries of 'Possibly', 'Probably' and 'Definitely' will be classified as 'Related'. Participants who experience the same event multiple times will be included in the most related category for tabulations by maximum relationship. Events with missing relationship will be considered as 'Related' but recorded as missing in the listings.

In summaries including intensity using CTCAE v5.0 grades, the following intensity categories will be summarized: 'Grade 1 -Mild', 'Grade 2 - Moderate', 'Grade 3 -Severe', 'Grade 4 – life threatening', 'Grade 5 – Death'. Participants who experience the same event multiple times will be included in the most severe category for tabulations by maximum intensity. Events with missing intensity will be considered as 'Severe' events for summary purposes but recorded as missing in the listings.

Adverse event summaries will be ordered alphabetically by System Organ Class (SOC) and decreasing frequency of PT within SOC in the group column for tables including event counts. For tables including only number and percentage of study participants, summaries will be ordered alphabetically by SOC and decreasing incidence of PT within SOC in the group column.

Listings of AEs and TEAEs will include the following:

- All AEs
- Incidence of all TEAEs
- All Related TEAEs
- All Serious AEs
- Discontinuation due to AEs

All listings (except incidence of all TEAEs) will be presented by study participant and treatment and will include the onset date/time and outcome date/time of the event, the event duration (derived), time to onset (derived), pattern of event, intensity, relationship, action taken, outcome and AEs that led to discontinuation.

The listing of incidence of all TEAEs will be presented by treatment and will include intensity, relationship, serious, number of participants reporting at least one TEAE within SOC/PT, number of individual occurrences of TEAE and site-participant number.

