13.1. Definitions

Term	Definition
Adverse Event (AE)	Any untoward medical occurrence in a subject to whom a medicinal product has been administered, including occurrences which are not necessarily caused by or related to that product. An AE can therefore be any unfavourable and unintended sign (including an abnormal laboratory finding), symptom, or disease temporally associated with the use of a medicinal (investigational) product, whether or not related to the medicinal (investigational) product.
Unexpected Adverse Event	An adverse event, the nature or severity of which is not consistent with the applicable product information (e.g., Investigator's Brochure for an unapproved investigational product or package insert/summary of product characteristics for an approved product).
Adverse Reaction (AR)	An untoward and unintended response in a subject to an investigational medicinal product which is related to any dose administered to that subject. The phrase "response to an investigational medicinal product" means that a causal relationship between a study medication and an AE is at least a reasonable possibility, i.e. the relationship cannot be ruled out. All cases judged by either the reporting medically qualified professional or the Sponsor as having a reasonable suspected causal relationship to the study medication qualify as adverse reactions.
Serious Adverse Event (SAE)	
A serious adverse event is any untoward medical occurrence that:
 
 • results in death • is life-threatening • requires inpatient hospitalisation or prolongation of existing hospitalisation • results in persistent or significant disability/incapacity • consists of a congenital anomaly or birth defect 
Other 'important medical events' may also be considered serious if they jeopardise the subject or require an intervention to prevent one of the above consequences.
 
NOTE: The term "life-threatening" in the definition of "serious" refers to an event in which the subject was at risk of death at the time of the event; it does not refer to an event which hypothetically might have caused death if it were more severe.

Serious Adverse Reaction (SAR)	An adverse event that is both serious and, in the opinion of the reporting Investigator, believed with reasonable probability to be due to one of the study treatments, based on the information provided.

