2.2.4 Safety endpoint(s)

2.2.4.1 Key safety endpoint(s)

The key safety endpoints of this study are the incidence/number of adverse events (AE), serious adverse events (SAE) and the severity of AEs from first dose of study treatment on D1 until D28. Each AE will be categorized as a Treatment Emergent Adverse Event (TEAE) or not. All cases will be assessed by the reporting medically qualified professional or Sponsor as to having a reasonable suspected causal relationship to study treatment or not and categorized on the eCRF as

1. Not related
2. Unlikely
3. Possible
4. Probable
5. Definitely

All AE/SAEs that fall into the last 3 categories are deemed as related to study treatment and will be classified as an Adverse Reaction (AR) or Serious Adverse Reaction (SAR) respectively.

Each SAEs will also assessed as to whether it was an unexpected SAR (Suspected Unexpected Serious Adverse Event, SUSAR)

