5 STUDY POPULATION CHARACTERISTICS

5.1 Participant disposition

Participants are considered **screenfails** if they were deemed not eligible for randomisation.

Since this is initially an in participant study the Nominal Days are not considered a scheduled protocol visit.

A participant who dies at any time during the study is considered as having **completed the study and primary assessment period**. If they discontinued early from planned active treatment duration (i.e. not including hospital discharge), the participant is considered as having **completed the study and primary assessment period, but not completed planned active treatment duration**.

In addition, a participant is considered to have **completed the study** if they have completed D28 and the follow-up visit. Participants can be discharged from hospital at any time, and as long as they have completed D28 and the follow-up visit, they have **completed the study**.

Participants have **completed primary assessment period** if they have:

- Arm A: completed up to 14 days of treatment with study drug followed by 14 days of either IV or oral prophylactic antibiotic treatment (as an in-participant or after discharge from hospital) AND completed D28 procedures
- Arm B: Completed up to 14 days of treatment with study drug (SOC+ 1 week of prophylactic antibiotic treatment) AND completed D28 procedures

Participants have **not completed primary assessment period**:

- are discontinued treatment prior to end of planned active treatment duration due to an adverse event - they may still complete D28 and/or follow-up visits
- discontinue treatment prior to end of planned active treatment duration as they meet an exclusion criterion (either newly developed or not previously recognized) that precludes further study treatment participation - they still may complete D28 and/or follow-up visits
- withdraw consent from being treated prior to end of planned active treatment duration – they may agree to complete D28 and/or follow-up visits
- Complete the treatment as planned but do not complete D28 procedures

Participants have prematurely **withdrawn from the study** if they:

- are lost to follow-up, after hospital discharge (i.e. do not complete D28 and follow-up visits or do not complete follow-up visit).
- Withdraw consent from being treated prior to end of planned active treatment duration and from D28 and follow-up visits

-

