7 MEASUREMENTS OF TREATMENT COMPLIANCE

Administration of study treatment (including the administration of appropriate antibiotics) will be performed at the study site under the supervision of the designated site personnel. Compliance will be monitored at the site through a review of the pharmacy and dispensing records to ensure that each study participant received the correct dose level.

Compliance with taking oral daily antibiotics for at least 14 days after hospital discharge in Arm A will be monitored during the planned phone call at D28. The taking of antibiotics after hospital discharge is not required for Arm B.

Any dosing deviations will be reviewed as IPDs at the DEM and assessed for possible impact on the PPS. If considered important, these deviations will be included in the summary and listing of IPDs.

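### The by-arm drug-related adverse event tables have no consistent reference product, so their Related rows cannot be compared between arms

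*SAP*

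**What the plan says.** SAP 2.2.4.1 has each event assessed as "having a reasonable suspected causal relationship to study treatment or not", on five categories from not related to definite. The top three make an event an adverse reaction, or a serious adverse reaction if it is serious. SAP 10.2 likewise lists relationship to study treatment among the items for each event. The same section dates pre-treatment events by "the first administration of study drug (Zilucoplan® for Arm A and IV antibiotic for Arm B".

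SAP 10 presents all safety summaries by treatment group and overall. Under SAP 10.2 these may include an overview with "serious TEAEs, discontinuations due to TEAEs, drug-related TEAEs, severe TEAEs and TEAEs leading to death", and also "Incidence of TEAEs by maximal relationship". A listing of related TEAEs is planned without that qualification. For the summaries, Possible and above become Related. Unlikely and Not applicable become Not related. A missing relationship becomes Related.

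Both arms receive prophylactic antibiotics. SAP 2 continues them until 14 days after the last Zilucoplan dose in Arm A and gives at most one week in Arm B.

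**The concern.** A row headed drug-related, with one column per arm, invites the reader to compare the columns. That is sound only if causality is judged against the same product, or the same set of products, in both arms. Here the term being judged changes meaning between sections, one arm receives no investigational product, and the product common to both arms is given for different lengths of time. The coding rules for blank and Not applicable entries bear most on the arm in which the relationship question is hardest to answer.

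At stake is the interpretation of the drug-related overview row, the by-relationship table and any adverse reaction counts by arm. The overall column has the same problem, because it could add Zilucoplan-related events in one arm to antibiotic-related events in the other.

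**Working it through.** There is no stated figure to reproduce. The main check sets the definitions side by side.

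| Place | Purpose of the text | Product meant |
|---|---|---|
| SAP 3.2.1.1 | anchor for relative day | "first dose of Zilucoplan® for participants randomised to Arm A and first dose of IV antibiotic for participants randomised to Arm B" |
| SAP 10.2 | boundary between pre-treatment and treatment-emergent events | "the first administration of study drug (Zilucoplan® for Arm A and IV antibiotic for Arm B" |
| SAP 5.1 | completion in Arm B | "Completed up to 14 days of treatment with study drug (SOC+ 1 week of prophylactic antibiotic treatment" |
| SAP 7 | compliance | "Administration of study treatment (including the administration of appropriate antibiotics) will be performed at the study site", with no limit by arm |
| SAP 2.2.4.1 and 10.2 | causality item | study treatment, product not named |
| Protocol 13.1, adverse reaction | causality | "An untoward and unintended response in a subject to an investigational medicinal product which is related to any dose administered to that subject" |
| Protocol 13.1, serious adverse reaction | causality | any one of the study treatments |
| Protocol 13.1, attribution scale | causality | the drug, not named |

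Two points follow.

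1. SAP 2.2.4.1 turns every event rated Possible or above into an adverse reaction, in either arm. The protocol ties an adverse reaction to an investigational product, which Arm B does not receive. An Arm B event judged due to the antibiotic is an adverse reaction under the SAP rule but not under the protocol definition.
2. Not applicable is given a coding rule in SAP 10.2 but is not among the five categories in SAP 2.2.4.1. The same Arm B event would count as Related if the field is blank and as Not related if Not applicable is entered.

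Antibiotic duration: 14 days of Zilucoplan plus 14 days gives up to 28 days in Arm A, against at most 7 days in Arm B.

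**Illustration.** The rates are assumptions. Let q be the share of patients with an antibiotic-related TEAE (equal in both arms) and z the share with a Zilucoplan-related TEAE, independent of q. If both products count in Arm A, its related share is 1 - (1 - z)(1 - q). With q = 10% and z = 5%, this is 1 - 0.95 × 0.90 = 14.5%.

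| Reading | Arm A | Arm B | A minus B (points) |
|---|---|---|---|
| 1. A judged on Zilucoplan, B on antibiotic | 5% | 10% | -5 |
| 2. A judged on both products, B on antibiotic | 14.5% | 10% | +4.5 |
| 3a. A judged on Zilucoplan, B entered as Not applicable | 5% | 0% | +5 |
| 3b. A judged on both products, B entered as Not applicable | 14.5% | 0% | +14.5 |
| 4. A judged on Zilucoplan, B left blank, 70% of B with any event (assumed) | 5% | 70% | -65 |

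Over q = 5% to 20% and z = 0% to 10%:

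- Reading 1 is z - q, from 0 - 20 = -20 to 10 - 5 = +5 points.
- Reading 2 is z(1 - q), from 0 to 0.10 × 0.95 = +9.5 points.
- Reading 3a equals z, from 0 to +10 points.
- Reading 3b runs from 1 - 1.00 × 0.95 = +5 to 1 - 0.90 × 0.80 = +28 points.
- Reading 4 is z - 70%, from -70 to -60 points.

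Reading 2 applies one consistent rule, but it relies on equal antibiotic rates. If the longer course gave 20% in Arm A against 10% in Arm B, with z = 0, the row would show +10 points with no Zilucoplan effect at all. In reading 3a the Arm B zero follows from coding and is not an observation.

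**The case against.** The strongest reply is that the arm-specific wording in SAP 3.2.1.1 and 10.2 only fixes a start date. Arm B needs one, and its first antibiotic dose supplies it. Neither passage tells investigators how to judge causality. This is correct. A reader might infer that an antibiotic reaction would be coded Not related in Arm A and Related in Arm B, so that Zilucoplan looks safer than control. The documents do not support that. It takes one of several conflicting definitions and treats a time anchor as a causality rule. SAP 7 points to counting the antibiotics in both arms, and the protocol's adverse reaction definition points to Zilucoplan alone; both can make Arm A look worse. Even under reading 1, Zilucoplan looks safer only when z is below q.

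It is also fair to say that the reach is limited. Protocol 4.2 gives the secondary safety endpoint as numbers of AEs and SAEs. Protocol 4.3 lists serious adverse reactions and SUSARs as exploratory. The key safety endpoints in SAP 2.2.4.1 are the incidence and severity of events. TEAEs by preferred term and arm are firmly planned, whereas the causality summaries are optional. No test or decision rule uses the Related row. The eCRF is not among the documents, so it cannot be checked whether it offers Not applicable, or how often Arm B entries would be blank.

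What remains is that the plan provides for the row by arm, does not say what it is relative to, and has coding rules that move Arm B events in opposite directions.

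**Conclusion.** The point holds as a comparability defect with no established direction. The reference product for relatedness is not consistently defined, so the by-arm drug-related and by-relationship summaries do not isolate harm from Zilucoplan. In the illustration the sign of the difference changes with the reading: -5, +4.5, +5 or +14.5 points, and -65 points if Arm B is left blank. These values rest wholly on assumed rates, and reading 4 also assumes that all Arm B relationship entries are missing. They show instability and do not estimate a bias.

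The all-causality, serious, severe and fatal TEAE tables do not use relatedness and are not affected. The change should be made because it is cheap and the row would otherwise be read as a comparison, but it does not threaten the main safety endpoints.

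**What to change.** In SAP 10.2, and to match in 2.2.4.1:

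- Define drug-related, adverse reaction and serious adverse reaction, for tabulation, as related to Zilucoplan. Tabulate them for Arm A only, and keep the rule that missing counts as Related for that table.
- Do not impute a missing relationship in Arm B as related to study drug.
- Make the relationship categories in the two sections agree, including whether Not applicable exists.
- If antibiotic-related events can be identified from the recorded data, show them separately for both arms under one identical missing-data rule, with a note on the different antibiotic durations. If they cannot be identified, say so and omit the table.
- State that the between-arm safety comparison rests on all-causality TEAEs and SAEs.

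The cost is SAP wording and table shells, with no new patients or procedures. The small loss is the single by-arm related row.
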